Trimosan is a vaginal gel, with a pH of 4, marketed to help restore and maintain the normal vaginal acidity and coats the walls of the vagina with a lubricating film that helps reduce odor causing bacteria (8). There are not yet any published trials regarding Trimo-San's efficacy.

Bacterial vaginosis occurs in a setting of vaginal pH > 4.5, with peak adherence to vaginal mucosa occurring at pH 5 -6 (6).

There are previous papers which suggest that acidifying gels have been able to treat BV and prevent recurrence compared to placebo in its ability to acidify the vaginal pH. (Successful treatment of bacterial vaginosis with a policarbophil-carbopol acidic vaginal gel; recurrent bacterial vaginosis: the use of maintenance acidic vaginal gel following treatment). Given these suggestive findings, it goes to follow that Trimo-san may also be effective in decreasing pH and bacterial vaginosis infections.

In one study, vaginal pH of 6.0 to 7.5 is strongly suggestive of menopause (13). While it is known that estrogen can reduce vaginal pH and that Trimo-san may potentially do the same, these creams have never been studied in the context of pessary users.

Objectives:

Study hypothesis: In postmenopausal pessary users, estrogen users will have a more acidic pH, less complaints of vaginal discharge/odor, and decreased rates of bacterial vaginosis, than trimosan users.

Primary objective: vaginal pH with both treatment arms, as measured by pH test strips

Secondary objective: to see difference of patient satisfaction between treatment arms as measured by an unvalidated vaginal symptoms questionnaire.

Tertiary objective: rate of bacterial vaginosis infection (to be diagnosed either by gram stain (Nugent Score) or BV Affirm.

Study Design:

- 1) Randomized controlled
- 2) Study duration: 1 year 3 years.
- 3) Subject duration: 3 months
- 4) Assessment of efficacy: Cost savings, future increase in compliance as less medication may be needed overall, possible decrease in bacterial vaginosis infection
- 5) Assessment of safety: Estrogen Side effects abnormal vaginal bleeding, nausea, breast tenderness, bloating. Otherwise, low risk study.

Study Population:

6) Number of subjects to be enrolled? 34. 17 in each arm. Power 80%. P value: 0.05 P value 0.5. Power 80%. Sample size calculated with the expectation that estrogen will drop vaginal pH to 5.5 and Trimosan will decrease vaginal pH to 4.5.

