- Recruitment: Will recruit 44 patients (assuming 15% non enrollment, and 15% drop out) This study will be open to all clinic patients at Harris Health (LBJ, Aldine, BT Clinics), UT Houston clinics (Memorial Hermann, Sugarland, Memorial City),
- 8) All participants will read and sign The Certificate of Informed Consent when they arrive at the designated testing site, prior to their participation in the research procedure. After the participants have finished their participation in the study, or once they have decided to withdraw from the study, they will be given a verbal and written debriefing statement.
- 9) Inclusion:
 - Postmenopausal female pessary user (ring with support pessaries only) 18 years and older. Postmenopausal defined as: 1) amenorrhea for a year 2) 3 months after surgical bilateral salpingo-oophorectomy
 - Is a new pessary user, or has not had a pessary for a year
- 10) Exclusion:
 - Pregnancy
 - o Persistent Bacterial Vaginosis infection in the first two clinic encounters
 - Currently on hormone replacement therapy
 - Previously on hormone replacement therapy in the past 6 months
 - o Currently on antibiotics
 - Patients with existing vaginal erosions/ulcerations

Study Procedures:

Estrogen Treatment Arm: Will use either Premarin or Estrace cream (dependent on patient's insurance). Premarin 1 gram every night for the first 7 days, then 0.5 grams twice weekly. Estrace cream – 2 grams daily for first 7 days, then 1 gram twice-weekly.

Trimosan Treatment Arm: ½ applicator for three times a week for 1st week, then ½ applicator for 2 times a week.

The procedures are different because of funding/resources differences at Harris Health Clinics versus UT clinics. At Harris Health, they can be fitted for a pessary, but they must then take a prescription to an outside pharmacy in order to buy their personal pessary, and must come back to have it placed. At UT clinics, they have a ready stock of pessaries that the patients may purchase at the time of their fitting.

For Harris Health and BT Clinics:

1st encounter - Clinic visit to fit pessary from kit, pessary will be ordered, vaginal pH collected, vaginal gram stain collected, pt will fill out questionnaire, and be randomized to a treatment arm.

2nd encounter – Clinic visit to have their own pessary inserted, and be advised treatment according to which treatment arm they were randomized to.

3rd encounter – Clinic visit in 2 weeks after pessary fitting to evaluate vaginal tissue and symptoms.

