4th encounter – Telephone call (6 weeks after personal pessary fitting) – to remind patient of their next visit and compliance with treatment.

5th encounter - 3 month clinic visit – vaginal pH to be collected, vaginal gram stain, will fill out questionnaire. Exit process explained and standard of care for pessary users will be continued.

For UT clinics:

1st encounter: Patients will be fitted for a pessary, and their own pessary will be placed, consented, fill out questionnaire, vaginal pH collected, BV affirm collected, randomized to a treatment arm, cream will be prescribed.

2nd encounter: Clinic visit in 2 weeks after pessary fitting to evaluate vaginal tissue and symptoms.

3rd encounter – telephone call – 6 weeks after initial pessary fitting to remind patients of next visit and compliance with creams

4th encounter – 3 month clinic visit: vaginal pH to be collected, BV affirm to be collected, will fill out questionnaire. Exit process explained and standard of care for pessary users will be continued.

Data and Safety Monitoring:

- 11) No adverse events expected
- 12) Plans for reporting unanticipated problems: ***
- 13) Safety monitoring plan periodic review by research team

Statistics: Level of significance p 0.5

Ethics

- IRB approval will be sought from CPHS.

The PI will see the patient. If the PI thinks that the patient may qualify for a study, she will communicate basic information to the patient and will inform the patient that the research coordinator will talk to her. The research coordinator will gather the pertinent information and will talk to the patient. If the patient agrees to hear about the study, the patient will be moved to a private room, if applicable. The PI will explain the consent form in the patient's native language provided that language is either English or Spanish. Other languages will require a consent form translated into the patient's native language. The PI will explain the study through the consent form page by page and will give the patient plenty of time to read the form and ask questions. If the patient agrees to participate then both the patient and the PI will sign the ICF and a copy will be given to the patient. Then in accordance with the protocol, the INC/EXC criteria will be revised and the screening test will be scheduled at the patient's convenience.

Data handling and record keeping

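### Recruiting 44 matches 34 plus 30%; with each 15% loss taken from those recruited or enrolled, 44 leaves about 31 to 32 evaluable, not the 34 tied to 80% power

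*Combined protocol and SAP*

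**What the plan says.** Study Population, item 6, gives the size and the power together: "Number of subjects to be enrolled? 34. 17 in each arm. Power 80" per cent. The same item gives the assumed means: "Sample size calculated with the expectation that estrogen will drop vaginal pH to 5.5 and Trimosan will decrease vaginal pH to 4.5". It states no standard deviation, and it prints the significance level two ways: "P value: 0.05 P value 0.5. Power 80" per cent.

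The Recruitment item that follows reads: "Will recruit 44 patients (assuming 15% non enrollment, and 15% drop out". It shows no formula, does not name the base of either percentage, and sets no separate target for patients with a usable primary measurement.

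Under Study Procedures, vaginal pH is collected at the first encounter and again at 3 months, in both clinic systems. For the UT clinics the last encounter is described as "3 month clinic visit: vaginal pH to be collected, BV affirm to be collected, will fill out questionnaire". Between those two points there is a 2-week visit to look at tissue and symptoms and a 6-week telephone call. Neither includes a pH measurement.

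**The concern.** A recruitment target is meant to leave the required number of patients after the expected losses. That calls for dividing the required number by the proportion retained. Adding the loss percentages to the required number falls short, because the losses then act on a larger group than the one they were computed from. The 44 looks like the second method.

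Primary-endpoint data are at stake. With one pH measurement on treatment, at 3 months, a patient who leaves before then contributes no on-treatment pH. The number of patients with a 3-month pH is therefore the number to set against the 80% power statement. If the plan's own loss rates do not leave 17 per arm at that visit, the stated power is not what the recruitment figure delivers.

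**Working it through.** **Inputs.** From item 6: 34 patients, 17 per arm, 80% power, assumed means 5.5 and 4.5 (difference 1.0). From the Recruitment item: 44 recruited, 15% non-enrolment, 15% drop-out.

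**Reproducing 44.**

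- Adding both losses to 34: 34 × (1 + 0.15 + 0.15) = 44.2, which rounds to 44. This matches.
- Multiplying up in sequence: 34 × 1.15 × 1.15 = 44.97, or 45.
- Dividing by retention in sequence: 34 / 0.85² = 47.06.
- Dividing by combined retention: 34 / 0.70 = 48.57, or 49.

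Only the additive method gives the printed integer. It closes if each 15% is a share of 34, that is 0.15 × 34 = 5.1 patients per loss: 44.2 − 5.1 = 39.1 enrolled, and 39.1 − 5.1 = 34. As ordinary rates, those losses are 5.1 / 44.2 = 11.5% of those recruited and 5.1 / 39.1 = 13.0% of those enrolled, not 15%.

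**Working forward from 44.**

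- Sequential losses: 44 × 0.85 = 37.4 enrolled; 37.4 × 0.85 = 31.8 with a 3-month pH. Shortfall 34 − 31.8 = 2.2.
- Both losses taken from 44: 44 × 0.70 = 30.8. Shortfall 34 − 30.8 = 3.2.
- If enrolment stops at 34: 34 × 0.85 = 28.9.

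**Recruitment consistent with 34 evaluable.** Sequential: 47 × 0.85² = 33.96 and 48 × 0.85² = 34.68, so 47 to 48. Both losses from the number recruited: 49 × 0.70 = 34.3, so 49.

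**Power, illustrative only.** The plan gives no SD, and two-sided alpha 0.05 is assumed because both 0.05 and 0.5 are printed. For a two-sample t-test with n per arm, power comes from the noncentral t distribution with 2n − 2 degrees of freedom and noncentrality (1.0 / SD) × √(n/2). The SDs for which 17 is the smallest n per arm reaching 80% run from 0.977 to 1.009.

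| Evaluable | Per arm | Power, SD 0.977 | Power, SD 1.009 |
|---|---|---|---|
| 34 | 17 | 82.5% | 80.0% |
| 32 | 16 | 80.0% | 77.4% |
| 31.8 | 15.9 | 79.7% | 77.1% |
| 31 | 16 and 15 | 78.6% | 76.0% |
| 30.8 | 15.4 | 78.4% | 75.7% |
| 28.9 | 14.45 | 75.6% | 72.8% |

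At the same SD, the loss against 17 per arm is 2.8 to 2.9 points at 31.8 evaluable, 4.1 to 4.3 at 30.8, and 6.9 to 7.2 at 28.9.

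**Scale.** At 17 per arm, an assumed SD of 0.9 gives 88.1% and 1.1 gives 72.9%. The unstated SD moves power more than this shortfall does.

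**The case against.** The best defence is that the plan is ambiguous rather than wrong. It never names the base of either 15%. If both were meant as allowances on 34, then 44 is right. Item 6 also labels 34 as the number to be enrolled, and 37.4 enrolled exceeds that. The gap is at most about three patients, and at the lower end of the compatible SDs 16 per arm still gives 80.0%.

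Some of this stands. The shortfall depends on how the percentages are read. Treating 34 as the evaluable number is an inference, drawn from the fact that the Recruitment item counts drop-out in reaching 44. The 28.9 figure applies only if enrolment is capped at 34, and the plan states no such cap. A power figure below 80% follows only if 17 per arm was the sponsor's own minimum; a different SD would give a different answer.

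It does not remove the point. A non-enrolment or drop-out rate expressed as a share of the final completers is not an ordinary rate, and the plan does not say that is what it means. Reading 34 as the number enrolled does not rescue the power statement either: with enrolment capped at 34, about 29 have a 3-month pH, and without a cap the count is again 31.8.

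**Conclusion.** The point holds. On the ordinary reading of the plan's own loss rates, recruiting 44 yields about 31 to 32 patients with a 3-month pH against the 34 on which 80% power rests, a shortfall of 2 to 3. That head count needs neither an SD nor an alpha. It rests on two readings: each 15% is a share of those recruited or enrolled, and 34 is the number needed after drop-out.

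The effect on power is modest: about 77% to 80% at 31.8 evaluable and 76% to 78% at 30.8, given two-sided alpha 0.05, a difference of 1.0, and an SD between 0.977 and 1.009. The missing SD and the conflicting alpha weigh more on the power statement. The correction is still worth making, because as written the recruitment figure and the power statement do not agree.

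**What to change.** In Study Population:

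- Label 34 as the evaluable target, meaning patients with a 3-month vaginal pH.
- State what each 15% is a share of. If the sponsor did mean shares of 34, say so explicitly, since that is the one reading under which 44 closes.
- Otherwise keep 44, restate the expected evaluable number as about 31 to 32, and recalculate power at that number from the sponsor's own SD and a single stated alpha. If 17 per arm was the minimum for 80%, expect a result slightly below 80%.

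This costs a few sentences and no extra patients. For reference, the recruitment figure consistent with 34 evaluable is 47 to 48 with sequential losses, or 49 if both losses are taken from the number recruited: 3 to 5 more than the 44 planned.

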Postmenopausal Pessary Users: Estrogen versus Trimosan

NCT03943823

Version Date: 09/28/2015

IRB Protocol

Protocol Title: Postmenopausal Pessary Users: Estrogen versus Trimosan

Principal investigator: [name]

Co-investigators: [name], [name], [name]

Study Coordinator: [name]

Population: Postmenopausal female new pessary users

Number of sites: Harris Health Clinics. Ben Taub Clinics. UT Houston Clinics

Study Duration: 6 months – 1 yr

Subject Duration: 3 months

General information:

Pelvic organ prolapse is seen in close to 96% of postmenopausal women (1). A pessary, which is a device placed into the vagina to support the prolapsing vaginal walls or to provide urinary continence, is commonly used to treat pelvic organ prolapse.

A common complication noted in pessary users is bothersome vaginal discharge. Vaginal discharge complication rates vary in different publications, ranging from 2.5% to 25% (2, 3). This complication may not cause pessary users to discontinue use (4); however, from clinical experience, it can be a source of embarrassment for the patient and a deterrent for family members to aid in self-care.

Little is known about the vaginal discharge in pessary users. In studies of vaginal discharge in pessary users, the symptomatic vaginal discharge is commonly attributable to bacterial vaginosis (5).

It is uncertain how vaginal pH is primarily established, but multiple factors are thought to contribute to establishing the acidic vaginal pH. Lactobacilli bacteria produce lactic acid, which is the primary acid in vaginal in normal vaginal secretions. The vaginal mucosa is also known to be an important source of lactic acid (12--6). While pH is known to alter the vaginal microbial environment, it has been shown that a pessary itself does not alter the microbial environment. (9)

The microbial composition between postmenopausal non pessary and pessary users have shown to be essentially similar (9).

Background Information:

Current popular creams used as an adjunct to pessary use are estrogen and trimo-san. Vaginally applied estrogen promotes epithelial cell growth and cellular maturation, decreases vaginal pH to premenopausal levels, and decreases severity of vulvovaginal symptoms (7)

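### The amenorrhea route to postmenopausal status has no condition on cause, so women who may not be estrogen deficient can enter and blur the population and the pH contrast

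*Combined protocol and SAP*

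**What the plan says.** Study Population, item 9, admits a "Postmenopausal female pessary user (ring with support pessaries only) 18 years and older" who is new to pessaries or has not had one for a year. The same item defines the key term: "Postmenopausal defined as: 1) amenorrhea for a year 2) 3 months after surgical bilateral salpingo-oophorectomy". The first route carries no condition on cause, age, ovarian status, hormone level or pH. The second covers only removal of both ovaries.

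Item 10 has two hormonal exclusions: "Currently on hormone replacement therapy" and "Previously on hormone replacement therapy in the past 6 months". The others concern pregnancy, persistent bacterial vaginosis, current antibiotics and existing vaginal lesions.

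Background Information supplies the rationale. It says that a "vaginal pH of 6.0 to 7.5 is strongly suggestive of menopause", and that vaginal estrogen "decreases vaginal pH to premenopausal levels, and decreases severity of vulvovaginal symptoms". The Objectives section states: "Primary objective: vaginal pH with both treatment arms, as measured by pH test strips".

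Study Procedures lists pH collection at the first encounter, ahead of randomisation, in both clinic systems. No entry criterion uses that value. The Statistics section gives only a significance level and plans no baseline adjustment or stratification.

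**The concern.** The protocol defines postmenopausal itself, so whoever meets the definition is eligible, and the ordinary meaning of the word does not narrow it. A woman who had a hysterectomy more than a year ago and kept working ovaries meets the first route, and no exclusion removes her. The same holds for a woman whose periods are stopped by a hormonal contraceptive or hormone-releasing device, because only hormone replacement is named.

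This looks like an oversight rather than a choice. The surgical route turns on loss of both ovaries, and the replacement-therapy exclusions keep out women already receiving hormones. Both rules treat estrogen status as what matters, and the first route alone leaves it open.

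Two things are at stake. The result may not describe the population in the title. And if some women have little room for pH to differ by product, the between-arm difference in the primary measure shrinks in a trial of 34.

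**Working it through.** **Step 1: does the text admit these women?**

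| Condition | Hysterectomy, ovaries working | Non-replacement hormonal product, no periods |
|---|---|---|
| Age 18 or older | met | met |
| A year of amenorrhea | met | met |
| Hormone replacement, current or past 6 months | not excluded | not excluded |
| Other exclusions in item 10 | unrelated | unrelated |
| pH threshold | none | none |

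Both qualify as written. The hysterectomy example is the clearer one. The hormonal example matters only for products that leave estrogen largely intact.

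**Step 2: the planned figure.** Study Population, item 6, gives 17 per arm, 80% power, and expected pH of 5.5 (estrogen) and 4.5 (Trimosan), a difference of 1.0. It gives no SD, and it prints the significance level as both 0.05 and 0.5. So 17 per arm cannot be reproduced from stated inputs. Taking two-sided 0.05 as an assumption, the SD can be solved for:

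SD = 1.0 × √(17/2) / (1.960 + 0.842) = 2.915 / 2.802 = 1.04 (normal approximation; 1.01 with the t distribution).

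The plan is thus consistent with an SD of about 1.0, which it does not state.

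**Step 3: illustration of lost contrast.** Suppose a fraction f of women in each arm has no between-arm difference in final pH. The documents give no value for f. The difference becomes 1.0 × (1 − f), and

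power = Φ[2.802 × (1 − f) − 1.960].

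- f = 0: Φ(0.842) = 80%
- f = 5%: Φ(0.702) = 76%
- f = 10%: Φ(0.562) = 71%

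The t-based calculation gives the same rounded values. Sample size per arm for 80% power is 17/(1 − f)²: 17/0.9025 = 18.8, so 19, at 5%; and 17/0.81 = 20.99, so 21, at 10%.

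**Step 4: sensitivity.** If the affected women end at 4.5 in both arms while other estrogen users average 5.5, the estrogen arm also becomes more variable. The average variance rises by f(1 − f)/2. Power is then about 75% at f = 5% and 70% at f = 10%.

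**Step 5: scale and direction.** One such woman per arm is 1/17 = 5.9%; two per arm is 2/17 = 11.8%. The factor (1 − f) applies whichever arm ends lower. This matters because the study hypothesis expects estrogen to be more acidic, while item 6 expects Trimosan to be lower.

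**The case against.** The strongest reply is that nothing shows such women would enrol in numbers. The documents give no age distribution, hysterectomy rate or contraceptive use. Enrolment is limited to new users of one pessary type. The Ethics section has the principal investigator judge who may qualify, followed by a review of the criteria and a screening test. This stands as a limit on size. It does not close the gap, because the content of the screening test is not given and the criteria being reviewed are the ones at issue.

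Three stronger readings are tempting, and the documents support none of them.

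- *The estrogen effect is known to be diluted.* A reader might infer this from the statement that estrogen lowers pH. But the planned 1.0-unit difference has Trimosan lower, and losing that difference requires these women to reach the same pH on either product. The documents do not say so; Trimosan is described as a gel of pH 4.
- *Power falls to a stated level.* At f = 20% the formula gives 61%, but that needs about 7 of 34 women (0.20 × 34 = 6.8), and nothing in the documents suggests it.
- *Entry should require pH 6.0 or higher.* Background Information calls 6.0 to 7.5 suggestive of menopause; it does not say that a lower value rules menopause out. Such a threshold would turn away truly postmenopausal women with lower pH. Background Information also places bacterial vaginosis at pH above 4.5, and only persistent infection is excluded, so one baseline strip does not isolate menopausal status.

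**Conclusion.** The point holds as a defect in the eligibility wording. The first route admits women outside the named population, and no other section removes them. Because randomisation spreads them over both arms, the consequence is a less well-defined population and a possible loss of contrast, not systematic bias between arms.

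The size is unknown. The figures of about 76% and 71% are conditional on four assumptions: 5% or 10% of women affected, no between-arm difference among them, two-sided 0.05, and an SD back-solved from 17 per arm. They show only that, in a trial this small, one or two such women per arm would be noticeable. They do not measure the trial's actual power. The wording should be corrected because that is cheap, not because a large loss has been shown.

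**What to change.** Reword the first route along these lines: *amenorrhea for at least 12 months with no other cause, that is, not explained by hysterectomy with an ovary retained or by a hormonal contraceptive or hormone-releasing device*. Add a prespecified age criterion, chosen and justified by the sponsor, by which women with a hysterectomy and a retained ovary qualify. Leave the bilateral removal route as it is, and do not add a pH threshold for entry.

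In the Statistics section, specify that the 3-month pH comparison is adjusted for the first-encounter pH (for example by analysis of covariance). This takes account of differing starting values. It does not restore a contrast that is absent in some women, so it complements the rewording and does not replace it.

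The cost is one amended eligibility criterion and one analysis sentence. No new test is needed, since the pH is already collected. The downside is that a few younger hysterectomised women or users of hormonal products become ineligible.

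### The exclusion for persistent bacterial vaginosis can only be met after randomisation, and at the UT clinics only after the assigned cream has been prescribed

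*Combined protocol and SAP*

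**What the plan says.** Study Population, item 10, lists as an exclusion "Persistent Bacterial Vaginosis infection in the first two clinic encounters". Study Procedures then sets out two schedules.

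- **Harris Health and BT clinics.** At the first encounter the gram stain is taken, and the "pt will fill out questionnaire, and be randomized to a treatment arm". The second is a "Clinic visit to have their own pessary inserted, and be advised treatment according to which treatment arm they were randomized to".
- **UT clinics.** The first encounter includes "BV affirm collected, randomized to a treatment arm, cream will be prescribed". The next is given as "2nd encounter: Clinic visit in 2 weeks after pessary fitting to evaluate vaginal tissue and symptoms".

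Neither schedule lists a BV specimen at the second encounter; the next one is at 3 months. The Ethics section adds that after consent "the INC/EXC criteria will be revised and the screening test will be scheduled", but no such step appears in either schedule.

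BV is the tertiary objective. The study hypothesis expects estrogen users to show "decreased rates of bacterial vaginosis, than trimosan users". Background Information ties BV to the primary outcome: "Bacterial vaginosis occurs in a setting of vaginal pH > 4.5". The protocol describes no blinding and defines no analysis set.

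**The concern.** An eligibility criterion should be settled before allocation. This one depends on what is found at a visit that follows allocation. If women who meet it leave the study or the analysis, the groups compared at 3 months are no longer the groups that were randomised.

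At UT the second encounter comes two weeks after fitting, with the cream already prescribed. If one cream clears BV faster than the other, more women are removed from the slower arm, and they are the women most likely to have BV at 3 months. The comparison of BV is then distorted, and to a smaller degree so is the comparison of pH.

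At Harris/BT the second encounter also follows randomisation, but treatment is first advised there, so BV found at that visit cannot reflect the cream. The same rule therefore does different things in the two systems. With no scheduled test and no blinding, a judgement of persistence could also be uneven or influenced by knowledge of the arm.

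**Working it through.** **1. Order of events.** No figure in the plan is in dispute; the point is sequence.

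| | Randomised | Assigned treatment begins | Second encounter | BV specimen then |
|---|---|---|---|---|
| Harris/BT | Encounter 1 | Advised at encounter 2 | Insertion of own pessary | None listed |
| UT | Encounter 1 | Prescribed at encounter 1 | Two weeks after fitting | None listed |

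The criterion needs information from encounter 2. In both systems that is after randomisation, and at UT it is also after prescription.

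**2. Does the screening sentence resolve it?** No. It mentions a check of the criteria and a test after consent, but neither schedule has a visit before randomisation. At UT, consent, BV sample, randomisation and prescription share one encounter.

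**3. Possible size, UT women.** The documents give no BV rate, no UT share and no encounter-2 test result, so every BV input here is assumed:

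- p = 0.30, baseline BV.
- q = 0.80 in arm A and 0.40 in arm B, persistence at encounter 2. So pq = 0.24 and 0.12.
- 3-month BV risk of 0.70 if persistent, and r otherwise.
- d = share of persistent cases detected and removed.

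All randomised: pq × 0.70 + (1 − pq) × r.
Retained: [pq(1 − d) × 0.70 + (1 − pq) × r] / (1 − pq·d).

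Scenario (a), creams act only through early persistence, r = 0.15 in both arms:
- A: 0.168 + 0.76 × 0.15 = 0.282
- B: 0.084 + 0.88 × 0.15 = 0.216
- True difference 6.6 points.

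Scenario (b), creams also act otherwise, r = 0.20 in A and 0.10 in B:
- A: 0.168 + 0.76 × 0.20 = 0.320
- B: 0.084 + 0.88 × 0.10 = 0.172
- True difference 14.8 points.

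| d | (a) A vs B, % | Difference | Loss | (b) A vs B, % | Difference | Loss |
|---|---|---|---|---|---|---|
| 0 | 28.2 vs 21.6 | 6.6 | 0 | 32.0 vs 17.2 | 14.8 | 0 |
| 0.25 | 25.5 vs 20.1 | 5.4 | 18% | 29.6 vs 15.6 | 14.0 | 5% |
| 0.5 | 22.5 vs 18.5 | 4.0 | 40% | 26.8 vs 13.8 | 13.0 | 12% |
| 1 | 15.0 vs 15.0 | 0 | 100% | 20.0 vs 10.0 | 10.0 | 32% |

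The zero in (a) follows from its assumption.

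**4. Whole trial.** Suppose half the women are at UT, the true risks are the same in both systems, d = 1 at UT and nobody is removed at Harris/BT. Under (a), arm A is (0.5 × 0.282 + 0.5 × 0.76 × 0.15) / (0.5 + 0.5 × 0.76) = 0.198/0.88 = 0.225, and arm B is 0.174/0.94 = 0.185. The difference is 4.0 of 6.6 points. Under (b) it is 13.0 of 14.8. The losses are 40% and 12%.

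**5. Lower baseline BV.** Under (b) with d = 1:
- p = 0.05: 22.0% vs 11.2%, a true difference of 10.8 points; 10.0 retained, loss 0.8/10.8 = 7%.
- p = 0.10: 24.0% vs 12.4%, a true difference of 11.6 points; 10.0 retained, loss 1.6/11.6 = 14%.

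**6. pH.** Assume persistent BV raises pH by δ = 0.5 to 1.0. The shift in the UT contrast is δ × {p(qA − qB) − (fA − fB)}, with f = pq(1 − d)/(1 − pq·d).
- d = 1: δ × 0.12 = 0.06 to 0.12.
- d = 0.5: fA = 0.12/0.88 = 0.136 and fB = 0.06/0.94 = 0.064, so the shift is δ × 0.047 = 0.02 to 0.05.

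The planned difference is 5.5 − 4.5 = 1.0 (Study Population, item 6). With half the women at UT and full detection there, the trial-wide shift equals the d = 0.5 result.

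**7. Women removed per 17 in each arm** = 17 × UT share × pq·d.
- All at UT, d = 1: 4.1 vs 2.0.
- Half at UT, d = 0.5: 1.0 vs 0.5.

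The recruitment target of 44 allows 15% for non-enrolment and 15% for drop-out. It does not say which, if either, covers these removals.

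**The case against.** The strongest reply is that the harm is conditional. Without a BV specimen at encounter 2, persistence cannot be shown by the protocol's own tests, so the rule may never remove anyone and the loss would be nil. That stands as a limit on the bias. It does not rescue the text: the criterion is then unworkable as written, and if staff apply it on symptoms, removals are unstandardised.

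The response-to-arm mechanism does not operate at Harris/BT, and the UT share is unknown. This also stands.

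The effect on the primary outcome is small, and the main distortion falls on a tertiary outcome that 17 women per arm estimate poorly. Under scenario (a) the standard error of the BV difference is √[(0.282 × 0.718 + 0.216 × 0.784)/17] ≈ 0.15, or 15 points, against an effect of 6.6. This bears on severity, but imprecision does not excuse an avoidable bias.

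Finally, a 30% baseline may be high. The only related rate in the documents is vaginal discharge in pessary users, 2.5% to 25%, which is not a BV rate but gives no reason to ignore lower values. Lower baselines shrink the loss, as step 5 shows, but leave the sequence conflict untouched.

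**Conclusion.** The concern holds. That the exclusion can only be met after randomisation, and at UT after prescription, follows directly from the protocol's own schedules and rests on no assumption. Whether bias results depends on whether women are actually removed and on whether early BV clearance differs by arm; the documents settle neither.

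Under the assumed inputs the loss in the UT BV contrast ranges from nil to about a third when the creams also act by other routes, and up to all of it when they act only through early persistence. The pH effect is minor against the planned difference. This should be fixed, because the contradiction is certain, the correction is cheap, and a few arm-related removals matter in a trial of 34.

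**What to change.** Reconcile item 10 with both visit schedules so that any BV exclusion the sponsor keeps uses only findings available before randomisation. Add a sentence defining the analysis set: BV status found after randomisation is not a reason to remove a woman from follow-up or analysis, and all randomised women are followed and analysed by assigned arm for pH, questionnaire and BV. Clinical care of a BV finding stays with the investigators and is not part of this change.

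Optionally, adjust for encounter-1 BV status together with clinic system, since the BV test differs (gram stain at Harris/BT, BV Affirm at UT).

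**Cost.** If post-randomisation BV is simply not used for removal, the change is wording only, with no extra visit or specimen. If a test-based exclusion is kept, randomisation may have to wait for the result. This applies in both systems, because each samples and randomises at the same encounter and no result time is stated. A single sample before randomisation also cannot show persistence, so the criterion itself would change and the population might too. Some women with BV would remain and add variability; the optional covariates absorb part of this but use degrees of freedom in a small trial.
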